12.3.2 Analyses of secondary and other efficacy analyses

All variables will be analyzed using descriptive statistics as described above.

12.4 Planned safety and other analyses

12.4.1 Safety analyses

Safety will be assessed following company and local regulations on an observational basis. Safety variables will be listed individually for detailed clinical review, when needed. Safety analyses will be performed on the SS. Adverse events will be summarized descriptively by system organ class (SOC) and preferred term (PT). The most recent version of the Medical Dictionary for Regulatory Activities dictionary will be used. Additional tables will summarize AEs by seriousness and relationship to study drug as well as separate tables for AEs leading to withdrawal from the study or SAEs. The specific set of AEs reported as injection reactions will also be summarized descriptively by SOC and PT along with their classification between injection site reactions and systemic reactions (then later being further classified as acute or delayed). Abnormal laboratory values, as well as lack of efficacy, are not considered to be an AE unless the physician assesses it as such. Complications that are not considered as worsening of the underlying disease but as an AE need to be reported on the intended worksheet. The information collected from the patient reported outcomes (eg, EQ-5D, HAQ-DI, Fatigue Assessment Scale, and arthritis pain VAS) are only considered to be an AE if the physician classifies it as such.

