4.2 Safety variable

• Incidence of AEs

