5 STUDY DESIGN

5.1 Study description

This is an observational, noninterventional, noncomparative, postauthorization safety study (PASS) to evaluate efficacy and long-term safety of CZP in adult patients with RA in need of treatment with a biologic.

The purpose of this study is to assess the clinical efficacy of CZP in achieving clinical remission with a DAS28 <2.6 after 2 years of therapy. The long-term safety will be evaluated, using reported treatment emergent adverse events.

The observational nature of the study leaves the therapeutic decision exclusively within the discretion of the treating physician. First the decision to treat the patient with CZP needs to be taken, before the treating physician can enroll the patient into this study. In addition, patient procedures and assessments will be performed in the frame of current standard clinical practice and as directed in the SmPC. Management of AEs will be handled according to drug safety regulations in Germany.

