6.3 Withdrawal criteria

Patients are free to withdraw from the study at any time without prejudice to their continued care.

If a patient discontinues for any reason, this reason must be recorded on the Study Completion Form. The physician will be encouraged to invite the patients who discontinue CZP therapy early to return to the clinic/practice for posttreatment. A Safety Follow-Up Visit will be performed 84 days after administration of the last dose of CZP.

In case a patient withdraws his/her data consent no further data should be collected or submitted on this patient or caregiver. If a patient is institutionalized, this should be recorded on the medical update form. Follow-up of hospitalized patients should continue during hospitalization. Hospitalization, by itself, does not necessarily constitute a reason for discontinuation.

The treating physician is free to add or withdraw any kind of medication, or to withdraw the patient from the study at his/her own discretion.

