12.1 Definition of analysis sets

The analysis set for the efficacy variables will be the Full Analysis Set. The Full Analysis Set is defined as all patients with a DAS28 ≥2.6 who took at least one dose of CZP and had at least one valid post-Baseline DAS28 value.

Note: the Full Analysis Set is defined in this way because patients who had a Baseline DAS28 value <2.6 would already be in remission. Therefore, the primary efficacy variable to reach clinical remission would not be defined.

The analysis set for the safety variables will be the Safety Set (SS), which is defined as all patients who took at least one dose of CZP.

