12.2 General statistical considerations

Statistical analysis and generation of tables, figures, and subject data listings will be performed using SAS[®] Version 9.1.3 or higher. All statistical tables and listings will use Courier New, font size 9.

All variables will be analyzed in an explorative manner using descriptive statistics only. Summary statistics will consist of frequency tables for categorical variables. For continuous variables, descriptive statistics (number of available observations, mean, and median, standard deviation, minimum and maximum) will be tabulated.

For analyses by visit, visit will be used as documented.

The Baseline value for all analyzed variables is the measured value at Visit 1 (V1) in Week 0.

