12.6 Planned interim analysis and data monitoring

The statistical analysis will proceed in several steps, based on interim analyses and a final analysis: interim analyses are planned to occur annually followed by a final analysis after

Confidential Page 36 of 89

completion of the study. The SAS® databases created for the interim analyses will contain all available data collected by visit up to and including around Visit 3 (from first interim analysis on), and Visit 6 (from second analysis on and applicable for any further analyses). The final database will be locked after the last patient last visit and will contain all study data.

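### The AE summaries named in the protocol are frequencies over all treated patients with no time base, although AE follow-up is unequal by design

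*Protocol*

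**What the plan says.** All references are to the protocol.

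- **Aim.** Section 4.2 lists one safety variable, "Incidence of AEs", with no time base. Section 5.1 states: "The long-term safety will be evaluated, using reported treatment emergent adverse events".
- **Summary.** Section 12.4.1: "Safety analyses will be performed on the SS. Adverse events will be summarized descriptively by system organ class (SOC) and preferred term (PT"). Section 12.2 adds "All variables will be analyzed in an explorative manner using descriptive statistics only" and "Summary statistics will consist of frequency tables for categorical variables". No rate per patient-time and no time-to-event summary is named.
- **Denominator.** Section 12.1 bases safety on the Safety Set, "which is defined as all patients who took at least one dose of CZP".
- **Follow-up.** Section 5.1.1 plans 116 weeks for a patient who does not stop early. For early stops, Section 6.3 says: "A Safety Follow-Up Visit will be performed 84 days after administration of the last dose of CZP". Section 8.3 agrees.
- **Later reports.** Section 10.2.2 extends SAE reporting to 84 days after each patient's end of study and sets no time limit for AEs that the physician thinks may be associated with the product.
- **Interim data.** Under Section 12.6 the interim databases "will contain all available data collected by visit up to and including around Visit 3 (from first interim analysis on"), and up to Visit 6 from the second analysis on. The final database holds all study data.
- **Deferral.** Sections 12 and 12.5 leave further statistical detail and dropout handling to the SAP.

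**The concern.** A patient who stops certolizumab pegol (CZP) at Week 4 is routinely observed to about Week 16 (4 + 12), yet counts in the denominator exactly like one observed for 116 weeks. Unequal follow-up is expected: Section 5.1.1 provides for stops for lack of efficacy, safety, personal reasons and physician decision, and Section 4.1.3 makes discontinuation in remission a study variable.

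In a post-authorization safety study of two-year use, readers will tend to take the AE percentage as a two-year incidence. On that reading it is too low, by an amount that depends on how many patients stopped and when. The same percentage can arise from different event rates, and percentages from interim and final tables rest on different mean follow-up. Without patient-years beside them, a reader cannot tell how much time a figure represents.

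**Working it through.** **The plan's own figures.** There is no expected AE incidence, AE precision or discontinuation rate to reproduce. The only sample-size figure concerns remission: 1.96² × 0.5 × 0.5 / 0.03² = 1067.07, rounded up to 1068, as Section 12.7 states. It does not bear on AEs.

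**Inputs from the protocol.** Full observation is 116 weeks (104 + 12). After an early stop it is 84 days = 12 weeks.

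**Assumed inputs.** D is the fraction stopping CZP by Week 104, with exponential stop times. P is the AE risk had everyone been observed for 116 weeks, with a constant hazard independent of stopping. Every early stopper is assumed to complete the 12 weeks.

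**Formulas.** μ = −ln(1−D)/104 and λ = −ln(1−P)/116 per week.
- Mean observed time = 12 + D/μ.
- Crude proportion = D − e^(−12λ) · [μ/(μ+λ)] · [1 − e^(−104(μ+λ))] + (1−D)·P.
- Relative understatement = 1 − crude/P.

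**Worked case, D = 30%, P = 50%.** μ = 0.00343 and λ = 0.00598. Mean observed time = 12 + 0.3/0.00343 = 99.5 weeks. Crude = 0.3 − 0.931 × 0.365 × 0.624 + 0.7 × 0.5 = 0.438. Understatement = 1 − 0.438/0.5 = 12.4%.

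**Relative understatement, constant hazard**

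| D | Mean weeks observed | P = 5% | P = 50% | P = 80% |
|---|---|---|---|---|
| 10% | 110.7 | 4.5% | 3.9% | 3.2% |
| 20% | 105.2 | 9.2% | 8.0% | 6.5% |
| 30% | 99.5 | 14.1% | 12.4% | 10.0% |
| 40% | 93.4 | 19.3% | 16.9% | 13.7% |
| 50% | 87.0 | 24.7% | 21.8% | 17.8% |

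The 10% mark is passed at D of about 22% (P = 5%), 25% (P = 50%), 30% (P = 80%) and 41% (P = 95%).

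**Sensitivity to AE timing.** The constant hazard is replaced by a Weibull form with the same 116-week risk. Results are for P = 5% / 50% / 80%.
- Early-weighted (shape 0.5): 8.9 / 7.3 / 5.2% at D = 30%; 12.2 / 10.0 / 7.2% at D = 40%.
- Late-weighted (shape 1.5): 17.4 / 15.8 / 13.6% at D = 30%.

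**Sensitivity to stop times.** Suppose stops are spread evenly over 104 weeks. Observed share of planned time = [(1−D)·116 + D·(52+12)]/116 = 0.87, 0.82 and 0.78 at D = 30%, 40% and 50%. At 5 events per 100 patient-years, with 365.25/7 = 52.18 weeks per year, the 116-week risk is 1 − e^(−0.05 × 116/52.18) = 10.5%. The crude figure is 9.1%, 8.7% or 8.2%, an understatement of 13% to 22%.

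**Interim tables.** Assume uniform entry up to a cut at T weeks. The observed share of a window of w weeks is then 1 − w/(2T): 0.885 (w = 12, T = 52), 0.750 (w = 52, T = 104) and 0.833 (w = 52, T = 156). These shares describe interim tables only.

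**The case against.** **It belongs to the SAP.** Detail and dropout handling are deferred, a rate is also a descriptive statistic, and Section 12.2 does not forbid one. A reader might infer that the plan rules out exposure-adjusted rates; it does not. What stands is that Sections 12.2 and 12.4.1 do choose the denominator and a frequency summary, and that choice lacks the time base that a long-term aim calls for.

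**The crude proportion is valid.** Section 10.1.1.1 limits treatment-emergent AEs to 70 days (5 half-lives) after the last dose, and the 84-day follow-up covers that window. The percentage therefore correctly describes treated patients as observed. This stands: the understatement exists only against a 116-week risk with everyone observed throughout.

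**Events can be recorded later.** Under Section 10.2.2, SAEs and suspected related AEs may arrive after routine follow-up. This stands too, so early stoppers do not simply become invisible. Routine collection of all AEs is still unequal.

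**The size is modest.** In the even-stopping example at D = 30%, the gap is 10.5 − 9.1 = 1.4 points. The 95% half-width at N = 1068 is 1.96 × √(0.105 × 0.895/1068), about 1.8 points. That is fair for a single table, but the shift is systematic and the interval would not reveal it.

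**Toxicity.** A reader might infer that patients leaving for toxicity make CZP look safer. That is not shown. Such a patient is counted for the event, Section 12.4.1 plans a table of AEs leading to withdrawal, and the working assumes that stopping is independent of events.

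**Conclusion.** The point holds in limited form. The protocol names only frequency summaries of AEs over all treated patients while routine AE observation differs by design. The resulting n (%) is sound as an as-observed description and too low if read as the 116-week incidence. Under a constant hazard and an AE risk of 5% to 80%, the relative understatement is about 3-5% at 10% stopping, 6.5-9% at 20%, 10-14% at 30% and 18-25% at 50%. It is smaller for early-onset AEs and larger for late-onset ones.

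Two stronger readings are not supported. A reader might infer that the long-term incidence will be understated by more than 10% under ordinary discontinuation. The protocol gives no discontinuation rate, and the 10% mark needs roughly 22-30% or more to stop under a constant hazard. A reader might also infer that the partial interim data depress the final incidence. They cannot, because the final database contains all study data; only the interim tables and their comparability with the final table are affected.

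Priority is minor to moderate: a cheap improvement, not an error that invalidates the safety analysis.

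**What to change.** In Section 12.4.1, for AEs, SAEs and AEs of interest, add exposure-adjusted incidence rates per 100 patient-years with 95% CI. The numerator is patients with a first event in the observed time. The denominator is time from first CZP dose to the earliest of first event, end of the AE collection window after the last dose, last contact or data cut-off. Events reported after that window would be listed separately so that numerator and denominator match. Show total patient-years beside the crude n (%) in every interim and final AE table.

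The cost is a person-time derivation and added columns. First-dose, last-dose and last-contact dates are needed for the planned follow-up anyway, and no visits are added. The downside is that a constant-rate summary can hide early clustering of events, so the crude n (%) should stay alongside.

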12.4.2 Other analyses

None.

12.5 Handling of dropouts or missing data

Handling of dropouts or missing data will be described in detail in the Statistical Analysis Plan.

12.6 Planned interim analysis and data monitoring

The statistical analysis will proceed in several steps, based on interim analyses and a final analysis: interim analyses are planned to occur annually followed by a final analysis after

Confidential Page 36 of 89

completion of the study. The SAS® databases created for the interim analyses will contain all available data collected by visit up to and including around Visit 3 (from first interim analysis on), and Visit 6 (from second analysis on and applicable for any further analyses). The final database will be locked after the last patient last visit and will contain all study data.

12.7 Determination of sample size

As no information on the expected remission rate for a 2-year study under real life conditions are available, an overall remission rate of 50%, which is the worst case for sample size calculation, was used for determination of sample size. Assuming this remission rate, a total of 1068 patients is sufficient to estimate with 95% confidence the overall remission rate with a precision of $\pm 3.0\%$. Furthermore, subgroups of about 500 patients are sufficient to estimate the remission rate for each subgroup (as defined in Section 12.3.1) separately with an adequate precision ($\pm 4.5\%$).

In case the overall remission rate is much lower or higher (15% / 85%) a total of 1068 patients is sufficient to estimate with 95% confidence the overall remission rate with a precision of $\pm 2.1\%$.

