5.1.2 Number of planned patients and sites

Physicians treating RA patients with biologics will be invited to participate in this PASS. Appropriate selection of the study sites will ensure collection of data representative for the general RA population.

The study will be conducted at approximately 160 sites in Germany. A total of 1068 patients are planned to be enrolled in this study, after the treating physician has made the decision to treat the patient with CZP.

Confidential Page 17 of 89

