5.2 Schedule of study assessments

The schedule of study assessments by visit are presented below.

Assessments ^a	Treatment period ^b							Safety Follow -Up		
Visit	V1	V2	V3	V4	V5	V6	V7	V8	V9	V10
Week	0	6	12	24	36	52	64	76	104	116
Written Data Consent ^c	X	X								
Demographics / Medical History	X									
Presence of Rheumatoid Factor	X									
Presence of anti-cyclic citrullinated peptide antibodies	X									
RA history	X									
Concomitant Medication	X	X	X	X	X	X	X	X	X	X
Adverse Events		X	X	X	X	X	X	X	X	X
Drug administration	X	X	X	X	X	X	X	X	X	
Joint scores (TJC, SJC) (28 joint count)	X	X	X	X	X	X	X	X	X	
Acute phase reactant (CRP or ESR)	X	X	X	X	X	X	X	X	X	
Morning stiffness	X	X	X	X	X	X	X	X	X	
Patient's Global Assessment of Disease Activity (VAS)	X	X	X	X	X	X	X	X	X	
Physician's Global Assessment of Disease Activity (VAS)	X	X	X	X	X	X	X	X	X	

Confidential Page 18 of 89

Assessments ^a	Treatment period ^b							Safety Follow -Up		
Visit	V1	V2	V3	V4	V5	V6	V7	V8	V9	V10
Week	0	6	12	24	36	52	64	76	104	116
Arthritis pain VAS	X	X	X	X	X	X	X	X	X	
Fatigue Assessment Scale	X	X	X	X	X	X	X	X	X	
HAQ-DI	X	X	X	X	X	X	X	X	X	
EQ-5D	X	X	X	X	X	X	X	X	X	
Sick leave	X	X	X	X	X	X	X	X	X	
Employment status and employability due to RA	X	X	X	X	X	X	X	X	X	
Information on subsequent RA treatment										X

CRP=c-reactive protein; EQ-5D=Euro Quality of Life – 5Dimensions; ESR= erythrocyte sedimentation rate; HAQ-DI; Health Assessment Questionnaire-Disability Index; RA=rheumatoid arthritis; SJC=swollen joint count; TCJ=tender joint count; V=Visit; VAS=Visual Analogue Scale

Confidential Page 19 of 89

^a Only if assessed as per current clinical practice. Since this is a noninterventional study, no additional diagnostic or monitoring procedure will be applied.

b Visits are recommended to be quarterly.

Written data consent will be obtained before any data are collected on study-specific forms. Written data consent may be obtained after the start of CZP treatment if the patient met all inclusion and exclusion criteria at the start of CZP treatment. For these patients, written data consent must be obtained at the start of Visit 2 and prior to conducting any clinical assessment at this visit.

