12.3 Planned efficacy analyses

12.3.1 Analysis of the primary efficacy variable

A patient is defined to have reached clinical remission if they show a DAS28 of <2.6. The absolute and relative number of patients in remission will be presented. Additionally, the respective 95% confidence interval (CI), constructed from an approximation to the Normal distribution, will be determined for the remission rate.

Evaluation will be done for subgroups defined by the following variables:

• Response at Visit 2 or Visit 3 (after approximately 6 and/or 12 weeks) defined by reduction in DAS28 by ≥1.2

Confidential Page 35 of 89

- Presence of relevant auto-antibodies at Baseline (cut-off depends on test used, eg, immunoglobulin M-RF enzyme-linked immunosorbent assay: ≥0.110 optimetric density; Latextest: >20IU)
- Presence of anticytoplasmatic antibodies (aCCP antibodies or anti-mutated citrullinated vimentin [MCV]); threshold for aCCP positive patient at Baseline >50Units; threshold for anti-MCV positive patient at Baseline >50Units/mL
- Pretreatments with other anti-TNF agents
- Pretreatments with other biologics
- Duration of RA disease (<2 years vs. ≥2 years)

The remission rates between subgroups and their associated 95% CIs will be compared numerically only.

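### The sample-size section quotes its precision for 1068 patients, but 1068 is the number enrolled and the efficacy set is smaller, so the plan does not ensure ±3.0% overall or ±4.5% in each subgroup

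*Protocol*

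**What the plan says.** Protocol Section 12.7 plans for "an overall remission rate of 50%, which is the worst case for sample size calculation". It then states: "Assuming this remission rate, a total of 1068 patients is sufficient to estimate with 95% confidence the overall remission rate" to within ±3.0%, and gives ±2.1% if the rate is 15% or 85%. For subgroups it says that "subgroups of about 500 patients are sufficient to estimate the remission rate for each subgroup (as defined in Section 12.3.1") with ±4.5%, which it calls adequate.

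Section 5.1.2 fixes the same figure as recruitment: "A total of 1068 patients are planned to be enrolled in this study".

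Section 12.1 analyses efficacy in the Full Analysis Set: patients with a Baseline DAS28 of at least 2.6 "who took at least one dose of CZP and had at least one valid post-Baseline DAS28 value". Footnote a to the schedule in Section 5.2 qualifies every assessment: "Only if assessed as per current clinical practice". The primary variable is read at Visit 9, around Week 104 (Section 4.1.1).

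Section 12.3.1 gives the remission rate a 95% interval "constructed from an approximation to the Normal distribution, will be determined for the remission rate", and lists six subgroup factors: early response, auto-antibodies, anti-citrullinated antibodies, prior anti-TNF agents, prior other biologics, and disease duration below versus at least 2 years. No expected share is given for any of them. Section 12.5 leaves dropouts and missing data to the SAP.

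**The concern.** The number needed for analysis and the number to be enrolled are the same, so the stated precision assumes that every enrolled patient enters the primary analysis. The protocol's own rules make that unlikely. The Full Analysis Set drops anyone without a valid post-Baseline DAS28 or with a Baseline DAS28 below 2.6, and the components of DAS28 are not mandatory at any visit.

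The subgroup sentence has a similar gap. It points to the subgroups of Section 12.3.1, but a category of about 500 out of 1068 exists only when a factor splits almost evenly, and nothing in the protocol supports that split.

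Interval width is the only justification given for 1068, and no hypothesis is tested. If the stated widths do not follow from the design, readers of the protocol are given a better precision than they should expect, most of all for subgroups.

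**Working it through.** **Inputs.** From Section 12.7: 95% confidence, rates of 50% and 15%/85%, 1068 patients, subgroups of about 500. From Section 12.3.1: Normal-approximation interval. From Section 5.1.2: 1068 enrolled. Loss rates and subgroup shares are not in the protocol; those below are assumptions shown as ranges.

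**Formulae.** Half-width h = z√(p(1−p)/n); required n = z²p(1−p)/h²; z² = 3.84146.

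**Reproducing the plan's figures.**
- ±3.0% at 50%: 3.84146 × 0.25 / 0.03² = 1067.07, rounded up to 1068.
- 1068 at 15%: h = 2.14%, stated as ±2.1%.
- 500 at 50%: h = 4.38%, inside the stated ±4.5%.

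All three agree.

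**How much loss the stated figures tolerate.** Reading them as rounded to one decimal:
- ±3.0% at 50% needs h below 3.05%: 3.84146 × 0.25 / 0.0305² = 1032.4, so 1033 patients. The slack is 1068 − 1033 = 35 patients, or 3.3%.
- ±2.1% at 15%/85% needs h below 2.15%: 3.84146 × 0.1275 / 0.0215² = 1059.6, so 1060 patients. The slack is 8 patients.

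**Overall half-width by assumed loss.**

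| Not analysed | n | h at 50% | h at 15%/85% |
|---|---|---|---|
| 0% | 1068 | ±3.00% | ±2.14% |
| 5% | 1015 | ±3.08% | ±2.20% |
| 10% | 961 | ±3.16% | ±2.26% |
| 20% | 854 | ±3.35% | ±2.39% |
| 30% | 748 | ±3.58% | ±2.56% |

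**Subgroups at 50%.** ±4.5% needs 3.84146 × 0.25 / 0.045² = 474.25, so 475 analysed patients in a category. For both levels of a two-level factor, the smaller must hold at least 475/1068 = 44.5%, and the two together use 2 × 475 = 950 patients. Reading ±4.5% as rounded (h below 4.55%) relaxes this only to 464 patients, or 43.4%.

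| Subgroup share | All 1068 analysed | 748 analysed (assumed 30% loss) |
|---|---|---|
| 50% | 534: ±4.24% | 374: ±5.07% |
| 25% | 267: ±6.00% | 187: ±7.17% |
| 10% | 107: ±9.47% | 75: ±11.32% |

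**The case against.** A reader might infer that Section 12.7 contains an arithmetic error, or that the design cannot deliver its precision unless all 1068 patients are analysed. The documents support neither reading.

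- Every stated figure reproduces.
- The widths are tightest at 50%, which Section 12.7 itself calls the worst case. Away from it, ±3.0% holds with fewer patients: after 10% loss if the rate is at most 34% or at least 66%, and after 30% loss if it is at most 22.6% or at least 77.4%.
- The Full Analysis Set needs only one valid post-Baseline DAS28, not a Visit 9 value. The SAP, which is not at hand, may keep patients without Visit 9 data in the denominator, for example as non-remitters. Only exclusions from the Full Analysis Set would then reduce n. Few Baseline exclusions should be expected, because inclusion criterion 3 asks for moderate to severe, active disease.
- The subgroup sentence is conditional: about 500 suffice. It does not promise 500 in each category. At a 15% rate, 242 patients already give ±4.5%.
- A reader might also want the interval adjusted for correlation within the roughly 160 sites. The protocol gives no intraclass correlation and no sign that it matters; that is a choice of method, not an error in Section 12.7.

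These points limit the conclusion but do not remove it. Section 12.7 commits to ±3.0% at 50% and to ±2.1%, not ±3.0%, at 15%/85%, and the second figure has the smaller slack. No missing-data rule restores patients outside the Full Analysis Set or makes a small subgroup larger. The reference to Section 12.3.1 attaches ±4.5% to subgroups whose sizes are nowhere justified.

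**Conclusion.** The point holds as one about sample-size assumptions. The protocol quotes precision for the enrolled number, analyses a subset, and allows nothing for the difference, so it does not ensure the stated widths. That they will be missed is not shown, because the protocol gives neither a loss rate nor subgroup shares.

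The overall effect is modest: at the 50% planning rate and assumed losses of 10% to 30%, ±3.0% becomes ±3.16% to ±3.58%. The subgroup effect is larger and needs no loss at all: ±6.0% for a 25% subgroup and ±9.5% for a 10% subgroup, against ±4.5%, again at 50%.

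Severity is moderate at most. Section 12.2 makes all analyses descriptive, Section 12.3.1 compares subgroups only numerically, no decision depends on ±3.0%, and the reported interval will show its actual width.

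**What to change.** Keep 1068 enrolled and reword Section 12.7:

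1. Say that 1068 is the enrolled number, state the number expected in the primary analysis with its basis, and give the half-width for it at 50% and at 15%/85%. If the expected number is uncertain, give a range (for example ±3.16% at 961 to ±3.58% at 748, at 50%).
2. Replace the ±4.5% statement for the subgroups of Section 12.3.1 with half-widths by share of the analysed set, for example 50%, 25% and 10%, and state that both levels of a factor reach ±4.5% at a 50% rate only with a near-even split.

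The cost is a change of wording and less favourable stated figures; no extra patients are needed. Holding 1068 analysed would instead take 1068/0.9 = 1187 enrolled at 10% loss or 1068/0.7 = 1526 at 30%, which is hard to justify for a descriptive study with so modest an overall widening.
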